9.4.8 Tabulation of Individual Participant Data

Individual subject data will be listed by measure and time point.

9.4.9 Exploratory Analyses

None.

10 SUPPORTING DOCUMENTATION AND OPERATIONAL CONSIDERATIONS

10.1 Regulatory, Ethical, and Study Oversight Considerations

10.1.1 Informed Consent Process

10.1.1.1 Consent/Assent and Other Informational Documents Provided to Participants

Consent forms describing in detail the study intervention, study procedures, and risks are given to the participant and written documentation of informed consent is required prior to starting any study procedure. IRB-approved consent forms will be provided to the IND, and will contain at a minimum the following information:

- a. That the trial involves research.
- b. The purpose of the trial.
- c. The trial treatment(s) and the probability for random assignment to each treatment.
- d. The trial procedures to be followed, including all invasive procedures.
- e. The subject's responsibilities.
- f. Those aspects of the trial that are experimental.
- g. The reasonably foreseeable risks or inconveniences to the subject and, when applicable, to an embryo, fetus, or nursing infant.
- h. The reasonably expected benefits. When there is no intended clinical benefit to the subject, the subject should be made aware of this.
- i. The alternative procedure(s) or course(s) of treatment that may be available to the subject, and their important potential benefits and risks.
- j. The compensation and/or treatment available to the subject in the event of trial-related injury.
- k. The anticipated prorated payment, if any, to the subject for participating in the trial.
- 1. The anticipated expenses, if any, to the subject for participating in the trial.

- m. That the subject's participation in the trial is voluntary and that the subject may refuse to participate or withdraw from the trial, at any time, without penalty or loss of benefits to which the subject is otherwise entitled.
- n. That the monitor(s), the auditor(s), the IRB/IEC, and the regulatory authority(ies) will be granted direct access to the subject's original medical records for verification of clinical trial procedures and/or data, without violating the confidentiality of the subject, to the extent permitted by the applicable laws and regulations and that, by signing a written informed consent form, the subject or the subject's legally acceptable representative is authorizing such access.
- o. That records identifying the subject will be kept confidential and, to the extent permitted by the applicable laws and/or regulations, will not be made publicly available. If the results of the trial are published, the subject's identity will remain confidential.
- p. That the subject or the subject's legally acceptable representative will be informed in a timely manner if information becomes available that may be relevant to the subject's willingness to continue participation in the trial.
- q. The person(s) to contact for further information regarding the trial and the rights of trial subjects, and whom to contact in the event of trial-related injury.
- r. The foreseeable circumstances and/or reasons under which the subject's participation in the trial may be terminated.
- s. The expected duration of the subject's participation in the trial.
- t. The approximate number of subjects involved in the trial.

10.1.1.2 Consent Procedures and Documentation

Consent forms will be IRB-approved and the participant will be asked to read and review the document. The Investigator will explain the research study to the participant and answer any questions that may arise. A verbal explanation will be provided in terms suited to the participant's comprehension of the purposes, procedures, and potential risks of the study and of their rights as research participants. Participants will have the opportunity to carefully

review the written consent form and ask questions prior to signing. The participants will have the opportunity to discuss the study with their family or surrogates or think about it prior to agreeing to participate. Participants will be informed that participation is voluntary and that they may withdraw from the study at any time, without prejudice. A copy of the informed consent document will be given to the participants for their records. The informed consent process will be conducted and documented in the source document (including the date), and the form signed, before the participant undergoes any study-specific procedures. The rights and welfare of the participants will be protected by emphasizing to them that the quality of their medical care will not be adversely affected if they decline to participate in this study.

Only authorized trial staff should obtain consent and the most currently approved IRB consent form must be used.

10.1.2 Study Discontinuation and Closure

The trial may be terminated at any time by the Sponsor if serious side effects occur, if the Investigator does not adhere to the protocol, or if, in the Sponsor's judgment, there are no further benefits to be achieved from the trial. In the event that the clinical development of the investigational product is discontinued, the Sponsor shall inform all trial Investigators/institutions and regulatory authorities.

To ensure subject safety, the following approach is included to allow suspension or termination of the trial should a serious unforeseen risk arise: in the event that there are 2 reports of the same serious, unexpected and related adverse event, the Medical Monitor will within 5 calendar days of notification of the second event make a recommendation to Sponsor senior management whether to enhance surveillance, suspend enrollment, halt all further exposures, terminate the trial or continue without change.

If suspended, the trial may resume once concerns about safety, protocol compliance, and data quality are addressed, and satisfy the sponsor, IRB and/or FDA.

10.1.3 Confidentiality and Privacy

Subject confidentiality and privacy are strictly held in trust by the participating Investigators, their staff, and the sponsor. This confidentiality is extended to cover testing of biological samples in addition to the clinical information relating to subjects. Therefore, the study protocol, documentation, data, and all other information generated will be held in strict confidence. No information concerning the study or the data will be released to any unauthorized third party without prior written approval of the sponsor.

All research activities will be conducted in as private a setting as possible.

The study monitor, other authorized representatives of the sponsor, representatives of the IRB, or the FDA may inspect all documents and records required to be maintained by the Investigator, including but not limited to, medical records (office, clinic, or hospital) and pharmacy records for the participants in this study. The clinical study site will permit access to such records.

The study subject's contact information will be securely stored at each clinical site for internal use during the study. At the end of the study, all records will continue to be kept in a secure location for as long a period as dictated by the reviewing IRB, or sponsor requirements.

Study subject research data, which is for purposes of statistical analysis and scientific reporting, will be transmitted to and stored at the sponsor or a subcontracted data management service. This will not include the participant's contact or identifying information. Rather, individual subjects and their research data will be identified by a unique study identification number. The study data entry and study management systems used by clinical sites will be secured and password protected.

10.1.4 Future Use of Stored Specimens and Data

This protocol does not include storage of any biological samples for future testing. All study data will remain de-identified and kept securely by the sponsor or by a qualified contracted vendor, for at least the period of time required by FDA.

10.1.6 Safety Oversight

Safety oversight will be under the direction of an internal Data Safety Monitoring Board (DSMB), chaired by the Sponsor's Chief Medical Officer. To ensure subject safety, the following plan is included to allow suspension or termination of the trial should a serious unforeseen risk arise.

• In the event that there are 2 reports of the same serious, unexpected and related adverse event, the Medical Monitor will convene the internal DSMB within 5 calendar days of notification of the second event for the purpose of determining whether to enhance surveillance, suspend enrollment, halt all further exposures, terminate the trial or continue without change.

The members of the DSMB will include the Medical Monitor, Executive VP of Clinical & Regulatory Affairs, Trial Biostatistician, and the lead Principal Investigator. Notification of any halt will be sent to all Investigators and IRB pending a final determination.

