2.3 Risk/Benefit Assessment

2.3.1 Known Potential Risks

The major risk associated with use of human tissue, even as a temporary, non-engrafting therapeutic, is the transmission of infectious agents. This risk is minimized through careful donor screening, Good Tissue Practices, and aseptic current Good Manufacturing Practices (cGMP) processing. Decellularization removes any risk of potential graft vs. host reactions. A review of the literature indicates that various cell and tissue based products tested as therapeutics for non-healing wounds show no differences in adverse event profile compared with SC alone. Experience with a 361 HCT/P version of TTAX01 (NEOX CORD) in treating DFU indicated that weekly application to large wounds may have been associated with a slightly higher rate of local tissue infection. This issue was not seen in Phase 2 testing at the lower frequency of every 4 weeks. Phlebotomy is performed twice, at baseline and end of study, which carries a minor risk of discomfort and possible hematoma. There have been no reported cases of infectious agent transmission in more than 53,000 distributed units of

NEOX®/CLARIX® 100 (trade name for amniotic membrane products) or NEOX®/CLARIX® CORD 1K® (trade name for umbilical cord products), nor have any remarkable adverse events or serious adverse events been reported related to these products. The protocol itself carries a small risk of delaying healing by virtue of excluding a range of alternative therapies, however, none of these is of proven benefit in healing the high grade ulcers under study.

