8.4.3.3 Expectedness

As with the use of any human tissue, the possibility of infectious agent transmission cannot be completely eliminated although all screening and microbial testing results were satisfactory for the tissue and tissue donor. Possible significant adverse events include microbial infection and transmission of viral disease.

Expected adverse events non-related to the product are those post-surgical conditions consistent with any dermal debridement and excoriation of an ulcer. Potential adverse events for all research subjects in this trial intrinsic to the nature of DFUs: bleeding, hematoma, cellulitis, pain, deteriorating ulcer exudation, erythema, edema, infections including deep tissue infections (osteomyelitis), and occurrence of new ulcers.

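### Sections 10.1.2 and 10.1.6 give conflicting versions of the only predefined, counted safety trigger, and its undefined *unexpected* condition appears to leave out the product's own major risk

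*Protocol*

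**What the plan says.** Section 10.1.6 places safety oversight under an internal DSMB chaired by the Sponsor's Chief Medical Officer. It adds a plan to "allow suspension or termination of the trial should a serious unforeseen risk arise". The condition and the first step are: "2 reports of the same serious, unexpected and related adverse event, the Medical Monitor will convene the internal DSMB within 5 calendar days". The board then determines which of five actions to take, from closer surveillance through to termination or no change.

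Section 10.1.2 repeats the condition and the five actions, but there "the Medical Monitor will within 5 calendar days of notification of the second event make a recommendation to Sponsor senior management". That section does not mention the DSMB.

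On the risks themselves, section 2.3.1 says: "The major risk associated with use of human tissue, even as a temporary, non-engrafting therapeutic, is the transmission of infectious agents". Section 8.4.3.3, under the heading Expectedness, says: "Possible significant adverse events include microbial infection and transmission of viral disease". Its next paragraph uses the word *expected* for post-surgical events not related to the product.

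**The concern.** A counted trigger is useful because it takes the decision to hold a review out of anyone's discretion. That works only if everyone can tell which events count and who must do what by when.

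The protocol leaves both points open. Two sections send the same trigger down different paths. The condition that selects events also turns on *unexpected*, while the section the protocol devotes to expectedness names the very infections that the product is most feared to cause. If two subjects had the same serious infection, judged related to TTAX01, a Medical Monitor following the text could reasonably conclude that no review was required. Another could conclude the opposite.

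**Working it through.** The protocol states no figure on this point, so the check is mainly a comparison of text.

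**Step 1: the two versions of the rule**

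| Element | Section 10.1.2 | Section 10.1.6 |
|---|---|---|
| Trigger | Two reports, same event, serious and unexpected and related | Same |
| Clock | 5 calendar days from notice of the second event | Same |
| Options | Five, from surveillance to termination | Same five |
| Due by day 5 | A finished recommendation | The board convened |
| Recipient or decider | Sponsor senior management | Internal DSMB determines |

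The first three rows agree and the last two do not. This conflict needs no interpretation.

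**Step 2: does infection transmission meet the trigger?**

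- *Serious*: would be met by any case that fits the definition in section 8.4.2.
- *Related*: possible under section 8.4.3.2, where the event must not be explicable by the subject's clinical condition.
- *Unexpected*: not defined anywhere in the protocol, and no reference list is named. There are two readings:
  - Reading A: an event listed under the heading Expectedness is expected. Infection and viral transmission then never count. The rule's stated purpose, an unforeseen risk, supports this reading, because section 2.3.1 foresees the risk.
  - Reading B: section 8.4.3.3 calls these events only possible, and attaches *expected* to non-related events. A related product infection could then count as unexpected.

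Reading A is the natural one given the heading, but the text does not settle it.

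**Step 3: is there another counted trigger?** No. Section 8.4.8 sets no events of special interest, and section 9.4.6 plans no interim analysis. Section 10.1.2 lets the Sponsor terminate for serious side effects, but as a discretion. Section 8.4.6 requires reporting of SAEs, not a board review.

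**Step 4: illustration of size.** Exposed subjects: n = 250/2 = 125 (total from the synopsis, 1:1 allocation from section 9.2). The protocol gives no rate p of one particular serious, related infection, so p is assumed. With independent subjects and at most one event each,

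P(at least 2) = 1 − (1 − p)^n − n·p·(1 − p)^(n−1).

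For p = 1%: 1 − 0.2847 − 0.3595 = 0.356.

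| Assumed p | P(at least 2 of 125) = chance the trigger is met, reading B | Chance the trigger is met, reading A |
|---|---|---|
| 0.5% | 0.13 | 0 |
| 1% | 0.36 | 0 |
| 2% | 0.72 | 0 |
| 3% | 0.89 | 0 |
| 5% | 0.99 | 0 |

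The choice between two readings of one undefined word therefore decides whether the rule can respond at all.

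**The case against.** The best defence is that the rule is one added plan for unforeseen risk, not the whole of safety oversight. Much of this stands:

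- Section 10.1.6 puts oversight generally under the board.
- Section 10.1.2 allows termination at any time for serious side effects, with no count and no expectedness condition.
- Section 8.4.6 sends every SAE to the Medical Monitor within 24 hours, and requires notice of potential serious risks to FDA and all investigators within 15 days.
- Section 7.1 has the investigator consider management changes for findings believed related to TTAX01. It gives a regulatory hold or a manufacturing deviation as further grounds for a pause, not as the only ones.
- Section 2.3.1 reports no transmission in more than 53,000 distributed units of related products, so true transmission may be rare.

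None of these requires the board to meet after repeated serious, related infections.

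On the deciders, the two steps could run in sequence, since the Medical Monitor sits on the board. But neither section says so, and the 5-day clock is attached to a different deliverable in each.

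A reader might infer more than the text supports:

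- *That the rule cannot fire for infection.* Reading B is open, so this is too firm.
- *That nothing else in the protocol covers such events.* The provisions above do, without a count or a duty to review.
- *That osteomyelitis and cellulitis show the same gap.* Section 8.4.3.3 lists them as intrinsic to the ulcer, section 2.3.1 does not call them the major risk, and the *related* definition would usually exclude them anyway.
- *That the board has no scheduled meetings.* Section 10.1.6 names none, but a charter or the governance section may set them.

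**Conclusion.** The concern holds on two counts. First, sections 10.1.2 and 10.1.6 contradict each other on who acts and what is due by day 5; this is plain from the text. Second, the only predefined, counted trigger either excludes serious product-related infection or leaves its inclusion to judgement during the event, by an internal board or by the Medical Monitor. The second count rests on how *unexpected* is read, and the defect is that the protocol does not say.

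The size cannot be fixed from the documents. The probabilities above depend on assumed rates, on all 125 subjects being exposed, and on cases being classed as the same event and judged related. They show what hangs on the definition; they do not predict infections in this trial.

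**What to change.** Put one identical trigger and one decision path in sections 10.1.2 and 10.1.6, stating who decides and what must be done by day 5. Word the trigger so that two reports of the same serious, related event convene the existing DSMB even if the event is listed in section 8.4.3.3. There are two ways to do this: drop *unexpected* from the condition, or define what it is judged against and state that serious, related infection or transmission counts.

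The sponsor may also consider whether a single suspected transmission should convene the board. That is an option and not needed to cure the defect.

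The cost is a wording change in two sections and possibly an extra ad hoc meeting of a board that already exists. Sample size, analysis and data collection are unaffected.

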10.1.7 Clinical Monitoring

Clinical site monitoring is conducted to ensure that the rights and well-being of trial participants are protected, that the reported trial data are accurate, complete, and verifiable, and that the conduct of the trial is in compliance with the currently approved protocol/amendment(s), with International Conference on Harmonisation Good Clinical Practice (ICH GCP), and with applicable regulatory requirement(s). A separate clinical monitoring plan will be developed by the Sponsor.

The clinical monitor will periodically inspect all eCRFs, trial documents, and research facilities associated with this trial at mutually convenient times during and after completion of the trial. The monitoring visits provide the Sponsor with the opportunity to evaluate the progress of the trial; verify the accuracy and completeness of eCRFs; ensure that all protocol requirements, applicable FDA regulations, and Investigator's obligations are being fulfilled; and resolve any inconsistencies in the trial records. This includes inspection of all documents and records that are required to be maintained by the Investigator, including but not limited to medical records (office, clinic, or hospital) for the patients in this trial. The names and identities of all research patients will be kept in strict confidence and will not appear on eCRFs.

10.1.8 Quality Assurance and Quality Control

TissueTech, Inc. or its designee shall implement and maintain quality control and quality assurance procedures with written standard operating procedures to ensure that the trial is conducted and data are generated, documented, and reported in compliance with the protocol, GCP, and applicable regulatory requirements. Specifically, this trial shall be conducted in accordance with the provisions of the Declaration of Helsinki, FDA regulations 21 CFR 50, 54, 56, and 312.50, and the ICH guidelines on GCP (ICH E6).

10.1.9 Data Handling and Record Keeping

10.1.9.1 Data Collection and Management Responsibilities

During the trial, the Investigator will maintain adequate records for the trial, including medical records, records detailing the progress of the trial for each patient, eCRFs, signed informed consent forms, investigational product disposition records, correspondence with the IRB/IEC, AE/SAE reports, and information regarding patient discontinuation and completion of the trial.

Data collection is the responsibility of the clinical trial staff at the site under the supervision of the site Investigator. Refer to the eCRF completion guidelines for eCRF completion, correction, and transmission procedures. The Investigator is responsible for ensuring the accuracy, completeness, legibility, and timeliness of the data reported.

All source documents should be completed in a neat, legible manner to ensure accurate interpretation of data. Hardcopies of study visit worksheets may be provided for use as source document worksheets for recording data for each participant enrolled in the study. Data recorded in the electronic case report form (eCRF) derived from source documents should be consistent with the data recorded on the source documents.

Clinical data (including adverse events (AEs), concomitant medications, and expected adverse reactions data) and clinical laboratory data will be entered via eDC into RAVE EDC, a 21 CFR Part 11-compliant data capture system provided by Medidata. The data system includes password protection and internal quality checks, such as automatic range checks, to identify data that appear inconsistent, incomplete, or inaccurate. Clinical data will be entered directly from the source documents.

10.1.9.2 Study Records Retention

All records and documents pertaining to the trial including, but not limited to, data and source documents, will be maintained by the Investigator for a period of 10 years after completion of the trial or for a period of at least 2 years following the removal of an IND, whichever is longer. If the Investigator retires, relocates, or for any other reason withdraws from responsibility of

keeping the study records, custody must be transferred to the Sponsor or to a person who will accept responsibility and is approved by the Sponsor. In order to avoid any possible errors, the Investigator will contact the Sponsor prior to the destruction of any trial records. The Investigator will promptly notify the Sponsor in the event of accidental loss or destruction of any trial records.

10.1.10 Protocol Deviations

A protocol deviation is any noncompliance with the clinical trial protocol or ICH GCP requirements. The noncompliance may be either on the part of the participant, the Investigator, or the study site staff. As a result of serious or repeated deviations, corrective and preventative actions are to be developed by the site and implemented promptly.

It is the responsibility of the site Investigator to use continuous vigilance to identify and report deviations. The Investigator may not deviate from the protocol without a formal protocol amendment having been established and approved by the Sponsor and an appropriate IRB, except when necessary to eliminate imminent hazards to the patient or when the change(s) involve only logistical or administrative aspects of the trial. A deviation may result in the patient having to be withdrawn from the trial, rendering that patient non-evaluable.

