3 OBJECTIVES AND ENDPOINTS

OBJECTIVES	ENDPOINTS	JUSTIFICATION FOR ENDPOINTS			
Primary					
To determine whether treatment of high grade DFU with standard care plus TTAX01 results in a higher probability of achieving complete wound closure over 26 weeks, compared with standard care alone.	Time from baseline to initial observation of healing, over 26 weeks, where healing has been confirmed at two consecutive visits each two weeks apart.	The endpoint complies with FDA guidance. Dropouts should be minimal during the first 26 weeks, but may increase thereafter. Analysis will use a Cox proportional hazard model			
Secondary					
To compare differences between treatment groups in proportions of wounds healed through 50 weeks	Proportions of wounds healed by Week 50	This endpoint provides insight into longer term benefits of the intervention			
To compare long term durability of closure between treatment groups	Proportions of wounds that re-ulcerate by Week 50	May provide insight into the quality of healing			
To compare limb preservation between treatment groups	Proportions of minor (portions of the foot) and major (ankle, above or below the knee) amputations following the initial procedure by Week 50	Each amputation risks loss of mobility, with consequent increased mortality			
To compare patient reported mobility (lower extremity function) between groups.	Total score on PROMIS Health Organization Neuro- QoL "Lower Extremity Function" at Study End.	The tool is an NIH validated measure of patient reported outcomes			
Safety					
To examine Quality of Life endpoints related to therapeutic intervention	Total score of quality of life assessment determined by Cardiff Wound Impact Schedule (CWIS) at Study End				
Proportion of subjects experiencing adverse events, by group	Spontaneously reported and elicited adverse events, coded in MedDRA				

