7.2 Participant Discontinuation / Withdrawal from the Study

All subjects have the right to discontinue their participation in the trial at any time. The Investigator may also withdraw a subject from the trial at any time if they deem it medically necessary. The reason for discontinuation should be documented and trial staff should attempt

to bring the subject in for an Early Termination Visit and perform all applicable assessments, as appropriate, listed under the End of Study Visit for discontinuations that occur during the Trial Period.

Subjects may be discontinued from the trial for the following reasons:

- Adverse Event (including illness)
- Subject withdrawal of consent
- The Sponsor or Investigator terminates the trial
- Lost to follow-up
- Product-related > Grade 2 skin or systemic allergic reaction (CTCAE criteria)
- Ulcer-related complications (i.e., life-threatening, infection-related sepsis complications)
- Limb amputation (i.e., full amputation involving the index ulcer anatomic location)

In the event of a subject's withdrawal, the Investigator will promptly notify the medical monitor and will make every effort to complete all procedures at the End of Study Visit. Even if removed subjects have been removed from the trial or if an adverse event remains ongoing, Investigators should follow up with subjects as per their standard medical practice.

Discontinued subjects will not be replaced. Simultaneous screening at multiple sites may result in an allowable modest over-enrollment.

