8.1.11 Early Termination Visit

If a subject is withdrawn from their randomized treatment for any reason, they should be encouraged to continue with the subsequent scheduled visits for observation. The Observational Period visits are particularly valuable in monitoring long-term adverse events, (e.g., unresolved ongoing adverse events, and new treatment related adverse events including limb amputation for ulcers that do not heal).

If a subject is being withdrawn from the trial, attempt to schedule an early termination visit at which the End of Study procedures are carried out (refer to Section 8.1.6). Complete procedures described therein and document the reason for the subject's withdrawal.

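### Sections 7.2 and 10.1.10 permit exit from the trial, not only from treatment, after sepsis, a product reaction, an index-site amputation or any deviation, so later amputations may go uncollected

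*Protocol*

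**What the plan says.** Section 7.2 opens its list with "Subjects may be discontinued from the trial for the following reasons", so the list concerns the trial and not only TTAX01. Three entries are clinical events: "Ulcer-related complications (i.e., life-threatening, infection-related sepsis complications", "Product-related > Grade 2 skin or systemic allergic reaction (CTCAE criteria" and "Limb amputation (i.e., full amputation involving the index ulcer anatomic location". On withdrawal the site tries to hold an exit visit with the End of Study assessments. After that the investigator follows the subject as in ordinary practice. No further protocol visit or data capture is described, and discontinued subjects are not replaced. Section 8.4.4 records events only up to the final study visit.

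Section 10.1.10 defines a deviation as any noncompliance by the participant, the investigator or site staff, and then says: "A deviation may result in the patient having to be withdrawn from the trial, rendering that patient non-evaluable".

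The other relevant provisions are:

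- Section 3 names a secondary endpoint: "Proportions of minor (portions of the foot) and major (ankle, above or below the knee) amputations following the initial procedure by Week 50".
- Section 9.3 puts all randomised subjects in ITT, uses ITT for all primary and secondary efficacy analyses, and excludes major deviators from PP only.
- Section 9.4.3 fills a missing Week 50 amputation status by LOCF.
- Section 9.4.2 censors healing times at early discontinuation.
- Section 7.1 says that stopping TTAX01 is not leaving the study.
- Section 8.1.11 says of subjects taken off randomised treatment that "they should be encouraged to continue with the subsequent scheduled visits for observation", and gives limb amputation as one reason. For those leaving the trial it tells sites to "attempt to schedule an early termination visit at which the End of Study procedures are carried out (refer to Section 8.1.6".

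**The concern.** Outcomes that were never collected cannot be restored by any analysis, so a statistical analysis plan could not repair this. Section 2.2 describes infection as a major step on the path to amputation, and Section 2.3.2 expects fewer major amputations as a long-term benefit of the product. Yet Section 7.2 permits observation to end at sepsis or at a first index-site amputation, when the limb is most at risk.

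The deviation ground is wider still. It covers site errors as well as subject behaviour, and it includes use of a therapy that Section 6.5 prohibits through Week 26. Whether to withdraw is left to judgement in an open-label trial (Section 6.3). The term non-evaluable has no counterpart among the Section 9.3 populations.

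At stake are the Week 50 amputation endpoint, long-term safety and, to a lesser extent, the censoring assumption behind the primary analysis.

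**Working it through.** **Step 1. The plan's own figure, to see whether withdrawals threaten power.** Inputs from Section 9.2: 40% and 65% healed, log-rank with the Freedman formula, 90% power, 1:1 allocation, 10% dropout.

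- Hazard ratio for healing: ln(0.35)/ln(0.60) = 2.055.
- Events: (1.960 + 1.282)² × (3.055/1.055)² ≈ 88.1, so 89. This takes alpha as 0.025 per tail. Read as two-sided 0.025, the inputs give 105 events and 112 per group, which does not match the plan.
- Per group: 89/(0.40 + 0.65) = 84.8. Multiplying by 1.10 gives 94, the stated figure; dividing by 0.90 gives 95.
- Power: 94.1% at 110 per group (stated 94%) and 96.4% at 125 (stated 97%).

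With 125 per group and assumed losses of 10%, 20% and 30%, power is 96.4%, 94.3% and 91.2%. This treats loss as unrelated to outcome. Lost power is not the main issue.

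**Step 2. Each exit followed to Week 50 for the amputation endpoint.**

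| Exit reason | Known at exit | What LOCF carries forward | What may be missed |
|---|---|---|---|
| Index-site amputation | The amputation is recorded | An event in the combined minor and/or major analysis | A later, more proximal amputation; this matters for major amputation reported separately |
| Sepsis, no amputation yet | No event | Free of amputation | Any later amputation |
| Product reaction (TTAX01 arm only) | No event | Free of amputation | Any later amputation |
| Deviation, either arm | No event | Free of amputation | Any later amputation |

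If exit fell at Week 8 or Week 16 (assumed times), 50 − 8 = 42 or 50 − 16 = 34 weeks of planned observation would be lost for that subject.

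**Step 3. Direction on the primary endpoint.** Censoring treats a subject who leaves as healing later at the rate of those who stay. As an illustration only, suppose the plan's 10% dropout fell entirely on subjects who would not have healed and who left before any healing occurred.

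- In the control arm alone: apparent healing 0.40/0.90 = 44.4%. The ratio of cumulative hazards is 1.050/0.588 = 1.79 instead of 2.06, which works against TTAX01.
- In the TTAX01 arm alone: apparent healing 0.65/0.90 = 72.2%. The ratio is 1.281/0.511 = 2.51, which works in its favour.

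The sign depends on which arm loses its failures, and the protocol does not tell us that.

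**Step 4. Can a count be given?** Section 2.2 reports two Phase 2 subjects with minor amputations (2/32 = 6.3%) and no major amputations (0/32). It does not say whether the minor amputations were at the index site or whether either subject was withdrawn. Neither proportion estimates the number of subjects who would leave under Section 7.2, and no rate of withdrawal for deviation is given.

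**Step 5. Section 10.1.10 beside Sections 7.2 and 9.3.** Section 7.2 does not list deviation as a reason. Under Section 9.3 a major deviator stays in ITT and leaves PP. Section 10.1.10 provides for the same subject to leave the trial and become non-evaluable. The provisions do not fit together and need to be reconciled.

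**The case against.** Several points on the other side stand.

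- Both rules are permissive. A reader might infer that later amputations are always lost; the text supports only that they may be.
- A reader might infer that Sections 7.1 and 8.1.11 flatly contradict Section 7.2. They mainly concern stopping treatment, and Section 8.1.11 provides separately for leaving the trial. The conflict is one of purpose.
- A reader might take loss of an ulcerated toe as the model case. It is unclear whether that is a limb amputation in the Section 7.2 sense. Section 4.1 allows minor amputation at baseline debridement, and Section 8.1.4 keeps subjects with confirmed new osteomyelitis in the trial with the initial procedure repeated. A toe loss would also already count in the combined analysis.
- Scaling the Phase 2 result (2/32 × 250 = 15.6) is tempting but unsupported, for the reasons in Step 4. Phase 2 also found no adverse event attributable to TTAX01, so exits for a product reaction may be rare.
- Section 10.1.10 is an operational sentence and redefines no population. Withdrawn deviators formally remain in ITT as censored or carried-forward values.
- That prohibited therapy would be used more often in non-healing controls is plausible, but the protocol gives no figure. A reader might infer that removing such controls flatters the product; through censoring it would do the reverse.
- The wrong pointer to Section 8.1.6 might suggest that PROMIS is lost at early exit. It is a slip: the same sentence, Section 7.2 and Section 8.1.4 all name the End of Study procedures, which include PROMIS.

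None of this supplies data capture after exit for sepsis, a reaction or a deviation, and none of it gives non-evaluable a meaning under Section 9.3.

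**Conclusion.** The point holds in a limited form. The protocol permits exit from observation for clinical events that precede or accompany limb loss, and for any deviation, without stating any collection afterwards. LOCF can then misstate Week 50 amputation status: as free of any amputation after exit for sepsis, a reaction or a deviation, and as free of a later major amputation after an index-site amputation. Censoring of the primary endpoint may be informative, in a direction that depends on who leaves.

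The clearest internal inconsistency is between Section 10.1.10 and Sections 7.2 and 9.3. The harm is bias rather than lost power. Its size cannot be stated from the protocol, because it depends on how often sites use the discretion and on how many amputations follow exit. The conclusion assumes only that exit ends protocol data collection, as Sections 7.2 and 8.4.4 indicate.

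**What to change.** 1. In Section 10.1.10, delete the sentence or replace it with: *a deviation does not by itself end follow-up; the subject remains in ITT*.
2. In Section 7.2, split the list to match the purpose of Sections 7.1 and 8.1.11. Reasons for leaving the study would be withdrawal of consent, loss to follow-up and termination of the trial. Adverse events, product reactions, ulcer-related complications and amputation would be events after which treatment may stop but observation continues.
3. For the second group, collect at least index-ulcer status, further amputations, serious adverse events and vital status to Week 50, by telephone or from records where visits are not possible.
4. Clerical: in Section 8.1.11, change the reference from 8.1.6 to 8.1.8.

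The cost is an amendment to the wording and modest site effort, since the visits are already in the schedule. These changes concern observation only; no rule on when treatment should stop is proposed.
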